1L therapy treatment characteristics	Forms analysis set cohorts, duration of treatment is descriptive outcome	
Abstracted Data Elements: drug and/or combination endocrine partner, date of initiation, date of discontinuation, total number of cycles received, dose at initiation, dose reductions, dose increases, rationale for dose increase/decrease, treatment interruptions (e.g., drug holiday), rationale for treatment discontinuation (e.g., progression, toxicity, patient choice)
 
Calculated Variables: duration of treatment with initial endocrine-based therapy

1L therapy laboratory monitoring	Descriptive outcome	
Abstracted Data Elements: frequency of CBC, cardiac monitoring using electrolyte panel, liver function panel monitoring during first 3 cycles of therapy, date of first CBC, electrolyte panel, ECG, liver function panel
 
Calculated Variables: Time to first test during 1L therapy

Variable	Role/Time Period	Operational definition
Clinical outcomes during initial endocrine-based therapy	Primary clinical outcomes, comparison outcome for palbociclib+LET [REDACTED] CCI	Abstracted Data Elements: provider assessed response to therapy (CR, PR, SD, PD), date of best initial response (CR, PR, SD), date of disease progression, Calculated Variables: duration of stable disease
Advanced/metastatic treatment patterns following discontinuation of initial endocrine-based therapy	Descriptive Outcome	Abstracted Data Elements: drug regimens received post discontinuation of initial endocrine-based therapy (chemotherapy, switch to alternative endocrine), date of initiation and discontinuation of treatment regimens received Calculated Variables: total lines of therapy received in the metastatic setting
Status at last follow-up	Descriptive outcome, death used as part of PFS calculation	Abstracted Data Elements: date of last follow-up, receipt of hospice care, receipt of palliative care, date of death (if deceased), cause of death Calculated Variables: See section 5.1.5

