8. Mean duration (days) of first treatment interruption

Treatment Discontinuation and Switching:

9. Frequency/proportion of patients who discontinued 1L at 3 month intervals (through 24 months)
10. Frequency of reported rationale(s) for discontinuation of 1L (scheduled duration of therapy completed, disease progression, toxicities/adverse events, patient request (not due to toxicity/adverse event/intolerability), pill burden/compliance, death, unknown, other)
 - a. Frequency of reported rationale(s) for patient request to discontinue therapy (quality of life, difficulty in attending to activities of daily living, no longer wishes to receive treatment, return to work, caregiver burden, financial challenges, unknown, other)
11. Frequency/proportion of patients not initiating subsequent therapy
12. Distribution of regimens received in second-line among patients who received subsequent therapy

Finally, the following variables and outcomes will be described to evaluate disease response rates among each cohort during 1L treatment.

1. Frequency/proportion of patients with disease response assessed
 - a. Frequency/proportion with disease response assessed but recorded response level not available in the medical chart

2. Frequency/proportion of patients experiencing a CR, PR, SD, PD among all patients (including patients for who response was not evaluable/available at the time of data cut off)
3. Frequency/proportion of patients experiencing objective disease response (CR or PR)
4. Frequency/proportion of patients experiencing clinical benefit (CR or PR or SD lasting >24 weeks)
5. Time to response assessment among patients with known response categorization

Outcomes (response rates) for therapies received following discontinuation of 1L treatment will also be reported

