7.2 SURVIVAL ANALYSIS

[figure not shown]
Survival analysis, also called time to event analysis, will be used in the current research to estimate the time to treatment discontinuation, time to progression, and PFS in 1L. This method of analysis is employed when non-informative right-censoring occurs as is the case for this study since not all patients will have discontinued treatment, progressed or died by the end of the study period. The Kaplan-Meier method (product limit estimator) will be used to generate median estimates of time to progression and PFS if median time is reached within the population. Survival curves will also be generated. In addition to calculating the median survival estimate, the life-table method will be used to estimate these time to event outcomes at successive 3 month intervals through 24 months post initiation of 1L.

The following lists the measurements to be conducted using survival analysis techniques:

1. Median time to treatment discontinuation
 - a. Proportion of patients (survival estimate and 95% confidence interval) who are still receiving 1L treatment at 3, 6, 12, 18, and 24 months post 1L initiation
 - b. Event = any treatment discontinuation for any reason, censor = patients who are still on 1L therapy at data cut-off
2. Median time to progression
 - a. Proportion of patients (survival estimate and 95% confidence interval) who are progression free at 3, 6, 12, 18, and 24 months
 - b. Event = any treatment discontinuation for disease progression, censor = patients who are still on 1L therapy or who discontinued therapy for any reason other than disease progression at data cut-off
3. Median progression-free survival
 - a. Proportion of patients (survival estimate and 95% confidence interval) who are progression free and alive at 3, 6, 12, 18, and 24 months

- b. Event = any treatment discontinuation for disease progression or death, censor = patients who are still on 1L therapy or who discontinued therapy for any reason other than disease progression or death at data cut-off
- 4. Proportion of patients alive at 3, 6, 12, 18, and 24 months following 1L initiation
 - a. Event = death, censor = date of last follow-up among patients who are not deceased

CC
I

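### SAP 7.2 item 3 is labelled progression free and alive, but its censoring rule drops deaths after a non-progression stop of 1L; the size and direction of the effect on PFS are conditional

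*SAP*

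**What the plan says.** SAP 7.2 sets out four time-to-event measures.

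- **Item 3a** reports the proportion "who are progression free and alive at 3, 6, 12, 18, and 24 months".
- **Item 3b, event clause:** "Event = any treatment discontinuation for disease progression or death".
- **Item 3b, censoring clause:** patients still on 1L, or those "who discontinued therapy for any reason other than disease progression or death at data cut-off". It does not say whether the censoring date is the day 1L stopped, the last contact or the cut-off.
- **Item 4** (proportion alive): "Event = death, censor = date of last follow-up among patients who are not deceased". Whether 1L has stopped plays no part.

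The introduction to 7.2 says the methods will "estimate the time to treatment discontinuation, time to progression, and PFS in 1L", and justifies Kaplan-Meier thus: "This method of analysis is employed when non-informative right-censoring occurs".

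SAP 5.1 Table 2 describes the follow-up status variables as "Descriptive outcome, death used as part of PFS calculation" and refers to a section 5.1.5 for the calculation; the public text has no heading with that number. SAP 5.5 defines progression only. SAP 7.1 item 10 lists the reasons for stopping 1L. They include toxicity, patient request, pill burden and death, and one sub-reason for patient request is "no longer wishes to receive treatment".

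**The concern.** The label promises a quantity in which every death counts. The rule counts a death only when it is tied to the end of 1L. A patient who stops for intolerance or by choice and then dies, with no progression recorded, is neither progression free and alive nor a PFS event. Her death date is nevertheless in the eCRF, and item 4 uses it.

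This matters for three reasons. Landmark PFS is a stated objective, and Protocol 8.1 designs patient selection around estimating PFS at 24 months. PFS and survival will be reported at the same landmarks from the same time zero, yet they will treat these deaths differently. And two programmers could read item 3b in two ways and produce different curves. The rule also relies on stopping being unrelated to prognosis, which SAP 7.2 asserts without argument and which is doubtful for stops due to toxicity or declining quality of life.

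**Working it through.** The documents give no figure derived from item 3b, so there is none to reproduce. The check has a textual part and a numerical part.

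**1. One patient through the rules.** She stops 1L for toxicity at month *s*, starts nothing else, has no recorded progression, and dies at month *d* > *s*.

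| SAP 7.2 rule | Classification |
|---|---|
| Item 3b, if *or death* means death as the reason for stopping | Censored |
| Item 3b, if *or death* means any death | Event by the first clause, censored by the second |
| Item 4 | Event at *d* |

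The first reading fits SAP 7.1 item 10, where death is a listed reason for stopping. It is consistent within item 3b, but yields on-treatment PFS, which the item 3a label does not describe. The second reading contradicts itself.

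**2. Direction.** Inputs: 24-month PFS of 64.3%, the benchmark in Protocol section 6 and SAP section 1. Assumptions: exponential hazards; 20% net non-progression stopping by 24 months; post-stop hazard of progression or death equal to *r* times the on-1L hazard.

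- On-1L hazard: λ = -ln(0.643)/24 = 0.0184 per month.
- Stopping hazard: δ = -ln(0.80)/24 = 0.0093 per month.
- Censoring at the stop gives exp(-24λ) = 64.3% for every *r*.
- Counting later events gives S = exp(-24(λ+δ)) + δ[exp(-24rλ) - exp(-24(λ+δ))]/(λ+δ-rλ).
- At *r* = 2: 0.5144 + 0.0093 × (0.4134 - 0.5144)/(0.0277 - 0.0368) = 0.5144 + 0.1031 = 61.8%.

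| *r* | Later events counted | Overstatement when censored at the stop (points) |
|---|---|---|
| 0.25 | 66.8% | -2.5 |
| 0.5 | 65.9% | -1.6 |
| 1 | 64.3% | 0 |
| 2 | 61.8% | +2.5 |
| 3 | 59.8% | +4.5 |

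With 10% to 30% stopping, the range is +1.3 to +3.9 points at *r* = 2 and +2.2 to +6.8 at *r* = 3. If stoppers are instead carried event-free to data cut-off (cut-off uniform over 6-46 months, 20% stopping), the estimate is about 67.7% whatever *r* is. That exceeds the value with events counted by 1.0 point at *r* = 0.25 and by 7.9 points at *r* = 3.

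**3. Size when only deaths are added back.** Simulation with the same λ, data cut-off uniform over 12-40 months, and assumed proportions of stoppers who die a mean of 3 months after the stop. The entries are the item 3b estimate (censored at the stop) minus the estimate that counts those deaths, in points, for 10% / 20% / 30% dying.

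| Stopping by 24 months | Surviving stoppers censored at the stop | Surviving stoppers followed, no progression recorded |
|---|---|---|
| 10% | 0.6 / 1.2 / 1.8 | -1.0 / -0.2 / +0.5 |
| 15% | 0.9 / 1.8 / 2.7 | -1.5 / -0.4 / +0.8 |
| 20% | 1.3 / 2.5 / 3.7 | -2.0 / -0.5 / +1.0 |

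If surviving stoppers are censored at a next regimen a mean of 2 months after the stop, the range is 0.4 to 3.3. Entries vary by about 0.1 between simulation runs. The two columns bracket the answer: the left lets survivors leave the risk set at once, and the right keeps them in it with nothing but death able to occur. The left column and the next-regimen variant also assume that those who die start no further regimen. Any who did would be censored before death under the proposed rule, which shrinks the effect.

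**4. Scale.** At 64.3% with n = 200 and no censoring, the standard error is √(0.643 × 0.357/200) = 3.4 points, and the 95% half-width is 1.96 × 3.4 = 6.6 points.

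**The case against.** The strongest defence is that on-treatment PFS is what was intended. SAP 7.2 speaks of PFS in 1L, the protocol's fourth objective concerns outcomes during treatment, and death is a listed reason for ending 1L. On that reading item 3b is coherent, Table 2 is satisfied by on-treatment deaths, and item 4 is simply a different endpoint. This largely stands as an account of intent. It does not make the item 3a label true, supply a censoring date, or make the non-informative assumption safe.

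A reader might go further than the documents allow in three ways.

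- **That PFS is overstated.** This does not follow. With censoring at the stop, it requires a post-stop risk above the on-1L risk. The documents give no such figure, and the sign reverses below *r* = 1.
- **That every date needed for a conventional PFS is already collected.** Death, last follow-up, 1L stop and later-regimen dates are. Progression dates are requested only during initial endocrine therapy (Protocol 8.3, SAP 5.5), so adding deaths alone can raise the estimate.
- **That no sensitivity analysis is planned.** Text after item 4 and after SAP 7.5 is blacked out, so this cannot be inferred.

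It is also fair that the affected group may be small. Protocol 8.3 allows letrozole continued alone after palbociclib to be recoded as a subsequent line, and those patients would be censored under either rule.

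**Conclusion.** The mismatch is established from the text: the item 3a label, the two clauses of item 3b, item 4 and Table 2 do not describe one endpoint, and the visible text does not resolve it.

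The bias is conditional. It is likely upward if patients who stop for toxicity or by choice fare worse than those on 1L, or if they are carried event-free to cut-off. Under the assumed stopping and death rates it is about 0.4 to 3.7 points when surviving stoppers are censored at the stop or soon after at a next regimen, and -2.0 to +1.0 points when they are followed with no progression recorded. The largest value is about 1.1 standard errors (3.7/3.4) and within the 6.6-point half-width. For a descriptive study this should be corrected, but it does not undermine the design.

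**What to change.** 1. Rewrite item 3b. Event: the first of documented progression or death from any cause, before any new anti-cancer regimen. Otherwise censor at the start of the next regimen or at last follow-up, whichever is first, and state that date explicitly.
2. Deal with progression between the 1L stop and the next regimen. Either extend the eCRF progression-date field to cover that interval, or state that such progression is not captured and limit the interpretation accordingly.
3. Report the current rule alongside, labelled on-treatment PFS and not progression free and alive, with its censoring date given.
4. Align Table 2 and its cross-reference with the revised definition.

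Cost: SAP wording, a programming change and possibly one eCRF field. Protocol section 9 puts the eCRF before the IRB, and Protocol 8.6 requires resubmission for changes arising from the pre-test, so a new field may need resubmission. The PFS figure may shift slightly, in either direction.

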7.4 OTHER MULTIVARIATE ANALYSES

CCI

Logistic

regression methods will be used to estimate both odds of disease response and odds of clinical benefit. Cox proportional hazard models will be used to estimate the risk of treatment discontinuation and risk of progression at selected time interval or over the entire treatment interval. For the Cox proportional hazards model a robust variance estimator to account for the clustering within matched sets will be employed as stratified analysis has been shown to result in biased estimation of the marginal hazard ratio.^{13,14} Covariates included in these models will be ones measured at treatment initiation or prior to treatment initiation, such as age continuous age or categorical age, ECOG-PS (0/1 vs ≥ 2), and sites of metastatic disease (bone only vs any visceral sites). Additionally, other covariates significant at the 0.20 alpha level for the univariate analyses may be included in the multivariable model, after which individual removal of clinically and statistically insignificant variables using backward selection will occur to allow for the most parsimonious multivariable model possible.

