7. RESEARCH QUESTION AND OBJECTIVES

The main objective of this study is to describe patient demographics, clinical characteristics, toxicity monitoring, treatment patterns and clinical outcomes among postmenopausal, female, HR-positive, HER2-negative, MBC patients receiving palbociclib+LET as initial endocrine therapy. Demographic and clinical characteristics and outcomes will be presented overall, and among groups for the following three planned primary grouping variables:

1. Visceral vs. non-visceral at the initiation of initial endocrine therapy for MBC.
2. Received prior neo/adjuvant endocrine therapy versus no prior neo/adjuvant therapy.
3. De novo metastatic disease versus ≤ 12 months disease free interval since prior neo/adjuvant treatment versus > 12 months disease free interval since prior neo/adjuvant treatment.

[figure not shown]

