2 STUDY DESIGN

Patient demographics, clinical characteristics, treatment patterns pre- and post-palbociclib, laboratory monitoring, dosing patterns (and rationale for dosing changes), and clinical outcomes, including disease response and PFS will be described for locoregional recurrent or metastatic patients receiving palbociclib+LET as 1L, [REDACTED]

[REDACTED] The data will be collected through a physician-led, retrospective chart review. Providers will identify patients meeting the study selection criteria and abstract data from his/her patients' medical records into an electronic case report form (eCRF). Cardinal Health will conduct data verification via telephone and electronic follow-up. [REDACTED]

CCI

[REDACTED]

- 1) Presence of visceral metastases at the initiation of initial endocrine therapy for MBC
- 2) Receipt of prior neo/adjuvant endocrine therapy
- 3) De novo metastatic disease, ≤ 12 months disease free interval since prior neo/adjuvant treatment, >12 months disease free interval since prior neo/adjuvant treatment

CCI

[REDACTED]

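### SAP 7.4 chooses covariates by univariate screening and backward elimination with no stay level or forced-in set, so the covariate effects it reports would be unstable and overstated

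*SAP*

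**What the plan says.** SAP Section 7.4 covers two logistic models ("regression methods will be used to estimate both odds of disease response and odds of clinical benefit") and Cox models for treatment discontinuation and progression. Covariates are to be measured at or before treatment initiation. An illustrative, open-ended list names age, with continuous or categorical coding left open, and "ECOG-PS (0/1 vs ≥ 2), and sites of metastatic disease (bone only vs any visceral sites". Beyond that list, "other covariates significant at the 0.20 alpha level for the univariate analyses may be included in the multivariable model". Then "individual removal of clinically and statistically insignificant variables using backward selection will occur to allow for the most parsimonious multivariable model possible".

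The visible text gives no significance level for staying in the model, does not say which variables are forced in, and describes no allowance for selection when estimates are reported.

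Protocol Section 7 sets out "three planned primary grouping variables": visceral versus non-visceral disease; "Received prior neo/adjuvant endocrine therapy versus no prior neo/adjuvant therapy"; and de novo disease versus a disease-free interval of up to 12 months versus a longer one. SAP Section 2 repeats them, the second as "Receipt of prior neo/adjuvant endocrine therapy". Only the first has a counterpart among the covariates named in 7.4, and it is coded differently there. Bone only versus any visceral leaves patients whose disease is neither visceral nor confined to bone in no category.

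Two further facts bear on the size of the problem. SAP Table 2 gives visceral disease, and receipt and duration of neo/adjuvant treatment, a subgroup/matching role. For the Cox model, "a robust variance estimator to account for the clustering within matched sets will be employed". The section between 7.2 and 7.4 and the opening of 7.4 are redacted.

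**The concern.** When the same data choose the covariates and estimate their effects, three things follow. Real but moderate effects are often lost. Those that survive are, on average, the ones that chance pushed upward. Ordinary intervals for the survivors treat the final model as if it had been fixed in advance.

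The factors the protocol singled out for presenting results could be absent from the adjusted models for no better reason than a univariate p-value. Age, ECOG-PS and metastatic site skip the screen, but nothing says they are protected from the later removal step. Because selection is run on each outcome, the models for response, benefit, discontinuation and progression may also end with different covariates, which makes them hard to read together.

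What is at stake is any statement about which patient characteristics go with response or progression. Protocol Section 6 gives understanding which patients benefit most as part of the reason for doing the research.

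**Working it through.** The plan has no figure to reproduce: the Protocol abstract says that a sample size calculation does not apply. The consequences were therefore computed from the plan's own rates plus stated assumptions.

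**Inputs from the documents**
- Cohort size 200 (SAP 2.1).
- Progression-free proportions from earlier studies (Protocol Section 6): 64.3% at 24 months, and 54.7% at 18 months at the low end. Events in 200: 200 × (1 − 0.643) = 71 and 200 × (1 − 0.547) = 91.
- Response rate from the feasibility query (Protocol 8.5): (126 + 340)/804 = 58%.
- Screen level 0.20 (SAP 7.4).

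**Assumptions.** Effect sizes, covariate prevalence, number of candidates and stay level. Protocol 8.7 defines significance at two-sided 0.05 but does not tie that to elimination, so stay levels from 0.05 to 0.20 were tried.

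**Step 1: the screen alone (time to event).** SE of the log hazard ratio = 1/√(events × p(1 − p)), with p the covariate's prevalence. P(fail) = Φ(1.282 − ln HR/SE). With 71 events, p = 0.5 and HR 1.5: SE = 0.237, ln HR/SE = 1.71, P(fail) = 0.335. Over 71-91 events and prevalence 30-50%:
- HR 1.25 fails the screen with probability 0.59-0.66.
- HR 1.5 fails with probability 0.26-0.39.
- HR 2.0 fails with probability 0.02-0.08.

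In the other direction, the chance that at least one of 10 independent null candidates passes is 1 − 0.8^10 = 0.89.

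**Step 2: elimination in closed form (time to event).** Take a balanced binary covariate kept if its estimate exceeds 1.96 × SE, with SE = 2/√events, and true HR 1.3 (ln 1.3 = 0.262).
- 80 events: SE = 0.224; P(kept) = 22%; average HR when kept 1.76; coverage given retention 88%.
- 160 events: SE = 0.158; P(kept) = 38%; average 1.52; coverage 93%.

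**Step 3: screen plus backward elimination (logistic simulation).** 1,500 runs per setting, n = 200, about 58% response, 10 correlated binary candidates (latent correlation 0.3), screen at p < 0.20, then removal on p-values alone.

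| True OR | Stay level | Dropped | Average OR when kept | Coverage when kept |
|---|---|---|---|---|
| 1.25 | 0.05 | 88.6% | 2.05 | 67.8% |
| 1.25 | 0.10 | 83.2% | 1.94 | 78.2% |
| 1.25 | 0.20 | 75.8% | 1.75 | 81.0% |
| 1.5 | 0.05 | 71.5% | 2.27 | 89.5% |
| 1.5 | 0.10 | 63.1% | 2.14 | 90.1% |
| 1.5 | 0.20 | 54.9% | 1.96 | 93.0% |
| 2.0 | 0.05 | 39.1% | 2.50 | 95.2% |
| 2.0 | 0.10 | 28.4% | 2.38 | 95.8% |
| 2.0 | 0.20 | 23.8% | 2.22 | 96.2% |

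The full pre-specified model on the same data covered 93.5-95.1% in every setting. The 67.8% figure rests on about 0.114 × 1,500 = 171 retained runs, so its Monte Carlo standard error is about √(0.678 × 0.322/171) = 3.6 points.

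**Step 4: effect on a treatment comparison.** n = 400, a null exposure forced in, confounded and not matched, true covariate OR 1.5 or 2.0. With selection, bias was 0.003 to 0.029 log-odds and coverage 93.7-94.7%. Without selection, bias was within 0.01 and coverage 94.1-94.8%.

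**The case against.** The best reply is that this is a descriptive study, that 7.4 holds its other multivariable analyses, and that no visible numbered objective asks for covariate effects. The protocol calls the three factors primary for presenting results, not for adjustment. The screen applies only to covariates beyond the named ones, so metastatic site, and visceral status through it, is not screened. The named list is open, so the other two factors are not barred from direct entry. Removal is worded as needing clinical as well as statistical insignificance, so p-values alone may not decide, and no 0.05 stay level is stated. At 160 events the closed-form coverage is already 93%. Different covariates for different outcomes are not in themselves an error.

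Most of this limits the point without removing it. The clinical criterion is undefined, so it adds judgement made after seeing the data. The drop rates and inflation persist at every stay level tried, and near-nominal coverage at larger effects does not undo the upward bias in the estimates.

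A reader might infer three stronger things that the documents do not support:
- That adjusted treatment comparisons keep residual confounding by the grouping factors. SAP Table 2 gives them a subgroup/matching role and the Cox model refers to matched sets, so a factor dropped from the outcome model need not be uncontrolled. Step 4 found little bias even without matching.
- That the logistic models lack a matched-set variance. The visible sentence mentions only the Cox model, but the adjoining text is redacted and may cover it.
- That the reported intervals are known to ignore selection. The visible part of 7.4 does not mention intervals, so this is silence and not a stated choice.

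**Conclusion.** The point holds in a limited form. SAP 7.4 leaves covariate choice to outcome-based screening and backward elimination with no visible stay level or forced-in set, and two of the three planned grouping factors are not named. The main harm is to the covariate effects that would be reported. With 200 patients, an odds ratio of 1.5 would be lost in more than half of studies and overstated by roughly a third to a half when kept (1.96/1.5 = 1.31; 2.27/1.5 = 1.51). Smaller true effects fare worse. The effect on a forced or matched treatment comparison is likely small, at most about 0.03 log-odds, or 3% on the odds-ratio scale.

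These sizes rest on assumed effect sizes, 10 candidate covariates, stay levels of 0.05 to 0.20 and removal by p-value alone. The direction does not depend on the exact values. This is a cheap improvement to secondary models, not a flaw in the descriptive objectives.

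**What to change.** Replace the screening and backward-selection sentence in SAP 7.4 with one covariate set forced into every 7.4 model and reported in full:
- exposure, where the model compares cohorts;
- age, continuous;
- ECOG-PS as already grouped;
- visceral versus non-visceral disease, coded as in SAP Section 2;
- prior neo/adjuvant endocrine therapy and de novo/disease-free-interval group.

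The last two overlap by construction, since de novo patients would have had no earlier neo/adjuvant therapy. They should be coded to allow for this, for example as one combined factor. The coding should also say where patients with neo/adjuvant treatment but no endocrine therapy belong, because the protocol and SAP word that contrast differently.

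If any selection is kept, state the stay level and the protected variables, give bootstrap intervals that repeat the selection in each resample, and label the results exploratory.

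The cost is SAP wording; Table 2 already abstracts or calculates every covariate. Intervals will be slightly wider than a pruned model would show. The set needs about seven parameters. At 71-91 progression events in one cohort, that is about 10 to 13 events per parameter (71/7 and 91/7). Clinical benefit could be tighter. If all stable disease in the feasibility query lasted over 24 weeks, benefit would be (126 + 340 + 232)/804 = 87%, leaving about 26 of 200 without it. A penalised fit of the same set would suit that case better than a return to selection.
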